#### **14.7 Insurance**

Subjects will be covered under Swedish Match's liability insurance policy through IF insurances. The certificate of insurance and an information leaflet containing essential information about the insurance coverage can be provided upon request. The participating subjects are also protected in accordance with national regulations, as applicable. The University of Gothenburg has a company insurance covering services performed at the test laboratory.

## 15 STUDY MANAGEMENT

### 15.1 Training of study site personnel

Prior to the enrolment of the first study subject, the PI will ensure that all study personnel are adequately trained and familiar with the CSP, related documents, and any study-specific procedures or systems.

Given the PI's prior experience with similar studies and familiarity with the IP, a formal study initiation visit will not be conducted. Instead, the Sponsor will ensure that all necessary study materials and documentation are provided, and available to support the site as needed.

The PI will ensure that all personnel involved in the study are fully informed of all relevant aspects of the study and have detailed knowledge of and training in the procedures they are to execute. Any new information relevant to the performance of this study must be communicated to the staff involved in a timely manner.

The PI will maintain a list of all personnel involved in the study, including their roles and delegated responsibilities. A current *Curriculum Vitae* will be available for key staff to whom study-specific duties are delegated.

### 15.2 Clinical monitoring

No monitoring activities will be conducted during this study. All QC and safety measures will be managed through internal procedures and regular reviews by the study staff. Any deviations or issues will be documented and addressed according to the CSP and applicable guidelines.

### 15.3 Source data documents

Source documents are all documents used by the Investigator that relate to the subject's medical history, verify the existence of the subject, the inclusion and exclusion criteria, and all records covering the subject's participation in the study. They include laboratory notes, memoranda, material dispensing records, subject files, *etc*. The Investigator should guarantee access to source documents to the IECs, if required.

### 15.4 Study agreements

The PI must comply with all the terms, conditions, and obligations of the clinical study agreement for this study. Agreements between the Sponsor and the PI must be in place before any study-related procedures can take place or subjects can be enrolled.

### 15.5 Study timetable and end of study

The study is expected to start in Q4 2025 and be completed by Q1 2026.

A subject is considered to have completed the study if they have completed all usage visits in the study (Visits 2-4). Each subject who completes the study will participate for a period of 3 weeks, not including the preceding screening period.

The end of the study is defined as the last visit, *i.e.*, the last usage visit (Visit 4), of the last subject participating in the study.

## 15.6 Termination of the study

The Sponsor reserves the right to terminate this study prematurely for any reasonable cause. Conditions that may warrant study termination include, but are not limited to, a decision by the Sponsor to suspend or discontinue development of the IP.

If the study is prematurely terminated or suspended for any reason, the Investigator should promptly inform the study subjects and ensure appropriate follow-up for the subjects.

## 15.7 Reporting and publication

### 15.7.1 *Clinical study report*

A CSR, in compliance with ICH-E3, describing the conduct of the study, any statistical analyses performed, and the results obtained, will be prepared by the PI. The CSR will be reviewed and approved by, at a minimum, the PI and the Sponsor.

### 15.7.2 *Confidentiality and ownership of study data*

Any confidential information relating to the IP or the study, including any data and results from the study, will be the exclusive property of the Sponsor. The Investigator and any other persons involved in the study are responsible for protecting the confidentiality of this proprietary information belonging to the Sponsor.

### 15.7.3 *Publication*

The results from this study may be submitted for publication at the discretion of the Sponsor.

## 15.8 Archiving

The PI is responsible for maintaining essential documents, (as defined in ICH E6 GCP, Section 8) for 10 years after the finalization of the CSR. This includes any original source documents related to the study. It is the responsibility of the Sponsor to inform the PI when these documents no longer need to be retained.

The Sponsor will archive the TMF in accordance with ICH E6 GCP, Section 8, and applicable regulatory requirements.

The completed CRF is the sole property of the Sponsor and should not be made available in any form to third parties, except for authorized representatives of appropriate Health/Regulatory Authorities, without written permission from the Sponsor.

## 16 DATA MANAGEMENT

The data management routines include procedures database setup and management, data entry and verification, data validation, QC of the database, and documentation of performed activities, including information on discrepancies in the process. The database will be designed in accordance with the CSP.

### 16.1 The CRF

Clinical data will be entered into a paper CRF, directly from the source documents or the dental chair. Source data are to be defined before the inclusion of the first subject (Section 15.3).

Authorized site personnel designated by the Investigator will complete data collection. Appropriate training and security measures will be completed with the Investigator and all authorized study personnel prior to the study being initiated.

### 16.2 The entering of data into the CRF

All written entries, corrections, and alterations in the CRF are to be made by the Investigator or designated site personnel. All data should be entered in English. The CRFs should be completed as soon as possible during or after the subject's visit. If some assessments are not done, or if certain information is not available, not applicable, or unknown, the Investigator or assigned clinical staff should record such information in the CRF.

The Investigator must verify that all data entries in the CRFs are accurate and correct, and the PI will manually sign the CRFs.

### 16.3 Medical coding

The PI will handle AEs and medical/surgical history, and no formal medical coding will be performed. All documents will be approved by the Sponsor prior to database lock.

### 16.4 Database lock

When all data has been entered and discrepancies solved, clean file will be declared, the database will be locked, and the data will be analyzed.

## 17 STATISTICAL METHODS AND DETERMINATION OF SAMPLE SIZE

The principal features of the statistical analysis to be performed are described in this section.

### 17.1 General

Descriptive analysis will be performed to calculate the mean  $\pm$  standard deviation. Statistical analysis between the different products will be conducted for the various variables using two-way ANOVA followed by Tukey's HSD test. The relationship between the different collected variables will be analyzed using Pearson correlation coefficient. All analysis will be performed using PRISM 8 (GraphPad Software, San Diego, CA, US). A p-value  $<0.05$  is considered statistically significant.

No adjustment for multiple comparisons will be made.

No imputation of missing data will be performed.

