## 7 STUDY OBJECTIVES AND ENDPOINTS

### 7.1 Primary objective

To compare the effects on dental plaque acidogenicity after short-term exposure to three different Dry 3 mg NPs [REDACTED].

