## 8 STUDY DESIGN

### 8.1 Overall study design and schedule of events

This is an open-label, randomized, 3-way crossover, single administration study designed to assess the effects on dental plaque acidogenicity after using Dry 3 mg NPs, [REDACTED] in current daily users of NP or tobacco-based snus. The IPs are one Dry 3 mg NP (reference product) and two prototype products [REDACTED]. [REDACTED]. [REDACTED]

The study will include 12 randomized and fully evaluable subjects. Healthy male and female subjects aged  $\geq 21$ - $\leq 55$  years who have used NP or tobacco-based snus for  $\geq 1$  year, with a minimum weekly consumption of 3 cans, may be eligible for participation. An effort will be made to randomize at least 3 female subjects (25%).

The subjects will visit the test laboratory on four occasions, with at least three days between each visit. Each visit will last approximately 1.5 hours. Consequently, each subject is expected to participate in the study for about two weeks, excluding the screening period.

The subjects will report to the test laboratory for a screening visit (Visit 1), which will take place within four weeks prior to the first usage visit (Visit 2). This screening visit will involve an eligibility check, including evaluations of smoking and oral tobacco/nicotine use, a brief oral examination, urine pregnancy testing (for women of childbearing potential only), and collection of medical history. Additionally, the salivary secretion rate, buffer capacity, and the number of cariogenic bacteria (*Streptococcus mutans* and lactobacilli) will be assessed.

Before each usage visit (Visits 2-4), scheduled at the same time of day for each subject, the subjects will refrain from approximal tooth cleaning for 24 hours and toothbrushing for 12 hours prior to the visits. Additionally, subjects will be instructed not to eat, drink, chew gum, use nicotine-containing products (including smoking), or engage in any other mouth-related procedures 1 hour before the visits. Subjects will use their regular toothbrush, which may be manual or electric, throughout the study. Urinary pregnancy tests may be conducted at Visits 2-4 for women of childbearing potential.

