### 17.2 Determination of sample size

No formal sample size calculation has been performed. Based on previous clinical studies using the method for dental plaque acidogenicity (studies SM17-02 and SM22-01) (5, 6), a total of 12 subjects are considered sufficient to generate data that can detect a clinically significant increase in plaque acidogenicity for the two prototype products versus the reference product Dry 3 mg NP.

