### 17.5 Analysis of the primary endpoint

#### 17.5.1 *Difference in dental plaque acidogenicity*

The primary endpoint is the difference in dental plaque acidogenicity, assessed by measuring pH in plaques after short-term exposure (45 minutes) to three different Dry 3 mg NPs. The assessment of dental plaque acidogenicity will be calculated at each time point and presented with summary statistics, including the average for all four sites and the average per site, as described in Section 17.1.

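### The two prototype-versus-reference contrasts that justify the sample size are not carried into the primary analysis, which prescribes all-pairs Tukey and then rules out multiplicity adjustment

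*Protocol*

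**What the plan says.** The design has a clear reference. Protocol section 8.1 states "The IPs are one Dry 3 mg NP (reference product) and two prototype products", and section 9.9 labels the Dry 3 mg pouch as the reference in the randomization key.

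Section 17.2 gives no formal sample size calculation. It considers 12 subjects enough for data that "can detect a clinically significant increase in plaque acidogenicity for the two prototype products versus the reference product Dry 3 mg NP". That is a many-to-one question with two contrasts.

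The visible primary objective in section 7.1 is broader: "To compare the effects on dental plaque acidogenicity after short-term exposure to three different Dry 3 mg NPs". Section 17.5.1 follows it with an endpoint that spans all the study pouches ("The primary endpoint is the difference in dental plaque acidogenicity, assessed by measuring pH in plaques after short-term exposure (45 minutes) to three different"), names no contrast, and sends the reader to section 17.1 for the method.

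Section 17.1 prescribes "Statistical analysis between the different products will be conducted for the various variables using two-way ANOVA followed by Tukey's HSD test". It sets p < 0.05 as the level that "is considered statistically significant", and then adds "No adjustment for multiple comparisons will be made". The statistical methods part of the synopsis repeats all of this.

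**The concern.** Two things do not fit together.

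First, the contrasts that carry the sample size rationale do not appear in the sections that govern the test. Tukey's HSD spreads its 5% error rate over three pairs. One of these, prototype A against prototype B, cannot show whether either prototype is more acidogenic than the reference.

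Second, Tukey's HSD is itself a multiplicity adjustment across product pairs, and the same section says there will be none. An analyst could follow either statement and claim to follow the protocol. The same data could then give a significant prototype-versus-reference result under one reading and not under the other.

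The study is framed as a risk assessment with 12 subjects. Under Tukey, the stake is avoidable loss of power to see an increase in acidogenicity. Under no adjustment, it is a false-positive rate above the stated 5%.

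**Working it through.** **No plan figure to reproduce.** Section 17.2 gives no effect size, SD or power, so the 12 cannot be re-derived. What can be computed is the relative cost of each reading.

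**Inputs**
- From the protocol: 12 subjects (8.1, 17.2); three products, each used by every subject (9.9); significance level 0.05 (17.1).
- Assumed: all 12 subjects complete; one pH summary per subject and product; two-sided tests (sidedness is not stated; Tukey's HSD is two-sided); a model with subject and product, so error df = (12 − 1)(3 − 1) = 22.
- Assumed because not given: true differences of 0.8, 1.0 and 1.2 within-subject SDs, shown as a range.

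**Critical values of |t|, 22 df**
- Unadjusted: 2.074.
- Dunnett, two contrasts sharing a control (correlation 0.5): 2.363.
- Tukey, three pairs: 95% quantile of the studentized range for 3 means, divided by √2, = 2.512.

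Tukey intervals are 2.512 / 2.363 = 1.06 times as wide as Dunnett intervals, about 6% wider.

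**Power for one prototype-versus-reference contrast.** This is the noncentral t with 22 df and noncentrality δ / √(2/12), where δ is in within-subject SDs. For δ = 1 the noncentrality is 1 / 0.408 = 2.45.

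| True difference (SD) | Tukey | Dunnett | Unadjusted |
|---|---|---|---|
| 0.8 | 31% | 36% | 47% |
| 1.0 | 49% | 54% | 65% |
| 1.2 | 67% | 72% | 80% |

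The gap between Tukey and Dunnett is about 5 points across this range. Expressed another way, a contrast with 80% unadjusted power has 71.3% under Dunnett and 66.3% under Tukey. One with 90% unadjusted power has 84.0% and 80.3%. In subjects, with 0.842 as the normal quantile for 80% power: 12 × [(2.512 + 0.842) / (2.363 + 0.842)]² ≈ 13.1, so about one extra subject.

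**Familywise error with no true differences** (1,000,000 simulated trials, 22 df)

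| Reading of 17.1 | Two reference contrasts | All three pairs |
|---|---|---|
| Tukey governs | 3.6% | 5.0% |
| No adjustment governs | 8.9% | 11.8% |

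Under Tukey the two contrasts that matter use 3.6% of the 5% allowed. Under no adjustment they exceed it.

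**Sensitivity.** With 20 df (period also fitted) the critical values are 2.530 for Tukey and 2.379 for Dunnett, and power figures calibrated to the same unadjusted power move by about 0.2 points or less.

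**The case against.** Several points on the other side are sound.

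- A reader might infer that the plan never names the contrast of interest. It does: section 17.2 and the synopsis name the two prototypes against the reference. The fault is only that this is not carried into 17.1 and 17.5.1. Text after the primary objective and endpoint is also redacted and may name a comparator, so its absence from those sections cannot be claimed.
- All-pairs testing matches the visible objective of comparing three products. Tukey is valid, and it still tests and estimates both reference contrasts with familywise error at or below 5% for a given pH summary.
- The power loss depends on Tukey-adjusted p-values being used. If the no-adjustment sentence governs, there is no loss, and moving to Dunnett would lower power (65% to 54% at one SD).
- A reader might infer that a significant prototype A versus prototype B result alone would make the primary endpoint positive and leave the 17.2 question unanswered. The protocol states no such rule, and both reference contrasts would still be reported. If the prototypes moved 0.5 SD in opposite directions from the reference, A versus B would be the only significant pair under Tukey in about 29% of trials. Nothing in the protocol suggests such shifts, and that difference would be real, not a false positive.
- The no-adjustment sentence might be meant only for multiplicity across time points, sites and endpoints. That would reconcile it with Tukey, but the sentence carries no such limit.
- Details of contrasts are often left to a statistical analysis plan. Here, however, the protocol itself fixes a procedure and then contradicts it.

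**Conclusion.** The point holds in a limited form. Sections 17.1 and 17.5.1 do not carry forward the two contrasts that section 17.2 uses to justify 12 subjects, and section 17.1 makes two statements about multiplicity that cannot both apply to the product pairs.

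The size is modest: either about 5 points of power per reference contrast relative to Dunnett, roughly one subject, or familywise error of about 9% (two contrasts) to 12% (three pairs) where 5% is intended. These figures rest on one pH summary per subject and product, 12 complete subjects, 22 df, two-sided tests and assumed effect sizes. They do not address multiplicity over time points or sites.

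The documents do not support saying that the contrast is absent from the plan, that Tukey is invalid, or that power is lost whichever statement governs. The change is worth making because it removes a contradiction in the primary analysis and needs only wording.

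**What to change.** In section 17.1, section 17.5.1 and the statistical methods part of the synopsis:

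1. Name prototype A versus the Dry 3 mg reference and prototype B versus the Dry 3 mg reference as the primary contrasts.
2. Test these two with Dunnett's procedure at two-sided 5% in place of Tukey's HSD. Two-sided testing should be stated, since 17.2 speaks of an increase and 17.1 is silent on sidedness.
3. For this primary comparison, delete the no-adjustment sentence or limit it explicitly to other analyses. Adding Dunnett beside it unchanged would leave the contradiction in place.
4. Report prototype A versus prototype B as a supportive estimate with a 95% CI.

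The cost is protocol wording, with no new data or subjects. Prototype A versus prototype B loses its multiplicity-controlled test. If the sponsor had intended unadjusted tests, Dunnett also gives up some power per contrast (80% becomes about 71%) in return for holding familywise error at 5%.

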## 8.2 Rationale for study design

This is an open-label, randomized, 3-way crossover, single administration study designed to assess the effects on dental plaque acidogenicity after using Dry 3 mg NPs, [REDACTED] in current daily users of NP or tobacco-based snus.

Randomization will be used to minimize bias in the assignment of subjects to an IP use sequence, increasing the likelihood that known and unknown subject attributes (e.g., demographic and baseline characteristics) will be evenly balanced.

A crossover design was chosen to yield a more efficient evaluation of NPs than a parallel study design, as fewer subjects are required since each subject will serve as their own control. To avoid carry-over effects, subjects will abstain from nicotine products (including smoking) for at least 1 hour prior to each IP use visit (Visits 2-4). Additionally, there will be at least three days between each of the three usage visits with single administration to allow for accurate assessment of dental plaque acidogenicity.

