## 9.9 Randomization

At Visit 2, subjects will be randomized to one of 3 use sequences. The following sequences will be randomized:

Sequence 1: A B C

Sequence 2: B C A

Sequence 3: C A B

Where

A = Dry 3 mg NP (reference)

B = Prototype A Dry 3 mg NP [REDACTED]

C = Prototype B Dry 3 mg NP [REDACTED]

As this is an open-label study, the IP use sequence to which each subject is allocated will be recorded in the CRF.

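### The protocol names a two-way ANOVA for a three-period crossover but not its factors, nor any subject, repeated-measures or period term; run as ordinary product × time, its product p-values can be badly too small or too large

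*Protocol*

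**What the plan says.** Section 8.1 describes the design: "This is an open-label, randomized, 3-way crossover, single administration study". Section 9.9 allocates the order of use: "At Visit 2, subjects will be randomized to one of 3 use sequences". The three orders are ABC, BCA and CAB. Section 8.2 defends the crossover over a parallel design because "fewer subjects are required since each subject will serve as their own control". Sections 8.1 and 11.1 schedule plaque pH before placement and at seven later times, so there are 8 readings per visit. Buffer capacity has 4.

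For inference, Section 17.1 says that comparisons are "conducted for the various variables using two-way ANOVA" with Tukey comparisons, in PRISM 8, and that p below 0.05 "is considered statistically significant". The synopsis repeats this. The primary-endpoint section (17.5.1) has plaque pH "presented with summary statistics, including the average for all four sites and the average per site, as described in Section 17.1". Sections 17.6.1 (buffer capacity) and 17.7.1 (saliva pH) refer back to 17.1 in the same way, and none of the three adds a model term. Subject as a factor, repeated measures, period and sequence appear nowhere in Section 17.

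**The concern.** The design earns its efficiency from comparisons within a person, and the stated analysis does not say that it makes them. A model with two factors cannot hold product, time, subject and period together, so each way of reading the sentence leaves out something the design calls for.

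The most damaging reading is an ordinary product × time ANOVA. It puts between-person variance into the error term. It also treats the 8 readings of one visit as 8 independent pieces of evidence on the product. The first fault makes the product test too conservative and the second makes it too liberal. Which one wins depends on variances that the protocol does not give. The study asks whether two prototypes lower plaque pH relative to the reference, so both a missed drop and a spurious difference matter. The study is also open-label. If the factors stay unnamed, the error term can be chosen after the data have been seen.

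**Working it through.** **Inputs from the protocol.** 12 evaluable subjects (Section 8.1); 3 products, 3 periods, 3 sequences (9.9); 8 plaque pH readings per visit (11.1), taken as the mean of the four sites (17.5.1); alpha 0.05 (17.1). Section 17.2 gives no effect size, SD or correlation and no sample-size calculation, so there is no figure to reproduce.

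**Assumptions.** Total variance is 1, split into shares S (between subjects), V (subject-by-visit) and R (residual within visit). There were 4,000 simulated null trials per scenario, with 4 subjects per sequence wherever a period trend was simulated.

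**Degrees of freedom**
- Values: 12 × 3 × 8 = 288.
- Ordinary product × time: 288 − 24 cells = 264, which is 3 × 8 × 11.
- Product × subject: 2 × 11 = 22. With period: 22 − 2 = 20.
- Buffer capacity, ordinary product × time: 3 × 4 × 11 = 132.

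**Expected mean squares, ordinary product × time, no product effect**
- Product: 8V + R.
- Error: S + V + R = 1.

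The test is too liberal when 8V + R exceeds S + V + R, that is when 7V > S, and too conservative when 7V < S. With 4 readings the turning point is 3V = S.

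| S / V / R (assumed) | 8V + R | Simulated type I error at nominal 5% |
|---|---|---|
| 0.7 / 0.02 / 0.28 | 0.44 | 0.5% |
| 0.6 / 0.02 / 0.38 | 0.54 | 0.8% |
| 0.6 / 0.05 / 0.35 | 0.75 | 3% |
| 0.7 / 0.1 / 0.2 | 1.0 | 6.5% |
| 0.5 / 0.1 / 0.4 | 1.2 | 9.4% |
| 0.5 / 0.2 / 0.3 | 1.9 | 22% |
| 0.5 / 0.3 / 0.2 | 2.6 | 32% |
| 0.4 / 0.3 / 0.3 | 2.7 | 34% |
| 0.3 / 0.3 / 0.4 | 2.8 | 35% |
| 0.2 / 0.5 / 0.3 | 4.3 | 51% |

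The simulated error rises with 8V + R, as the formula predicts.

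**One time point, unpaired.** Here the error goes only one way. Type I error was 0.0% to 2.5%. For 0.5/0.3/0.2 and a product shifted by 0.6 SD, power was 0.18, against 0.50 with subject blocked.

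**Readings that keep the pairing.** With product × subject at one time point, or a repeated-measures product × time ANOVA, and no period effect, type I error was 4.4% to 5.6%.

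**Period left out.** Assume period means of 0, 0.25 and 0.5 SD.
- The deviations from their mean are −0.25, 0 and 0.25. The period sum of squares on visit means is 12 × (0.0625 + 0 + 0.0625) = 1.5.
- Left in the 22-df error, it adds 1.5 / 22 = 0.068 to a mean square that should be V + R/8.
- For 0.6/0.02/0.38 that mean square is 0.02 + 0.0475 = 0.0675, so it about doubles. Simulated type I error fell to 0.3%.
- For 0.2/0.5/0.3 it is 0.5 + 0.0375 = 0.5375, so it rises by about an eighth. Simulated type I error was 3.9%.
- Over all scenarios and both paired readings the range was 0.3% to 4.4%.

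**Subject + period + product on visit means (20 df).** Type I error was 4.3% to 5.8% in every scenario run, with and without the trend. With the trend and a 0.6 SD shift, power was 0.68 against 0.60 without the period term (0.5/0.3/0.2), and 0.96 against 0.90 (0.5/0.1/0.4).

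**The case against.** The strongest reply is that the protocol does not leave subject out; it leaves the factors unnamed. Sections 17.5.1, 17.6.1 and 17.7.1 speak of results time point by time point. If the ANOVA is run that way, time cannot be a factor, and subject is a natural second one. The pairing is then kept and the 264 degrees of freedom do not arise. This stands. A reader might infer that the model contains neither subject nor period, and that every product p-value therefore has the wrong error term. The text does not support that. Mucosal effects and the salivation VAS are also planned as descriptive in their own sections (17.6.2 and 17.6.3), and the VAS has one reading per visit.

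Second, Section 17 announces only that "The principal features of the statistical analysis to be performed are described in this section", and an analysis plan that is not shown may supply the rest. This stands for details such as the degrees-of-freedom method. It does not dispose of the point, because the protocol names a method, and no two-factor version of it fits the design in full.

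Third, the three sequences form a Latin square. With equal numbers per sequence, an additive period effect does not bias the product means, and leaving period out costs only precision. This also stands, with a limit: Section 9.9 does not state equal allocation, and Section 9.8.3 provides for replacement only before product use, so later withdrawals can upset the balance.

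Fourth, the variance shares are assumed, and some scenarios fall below 5%. That is correct. The calculation shows that the error is uncontrolled; it does not show that this trial's test will be liberal. Nor can it be said that the basis for 12 subjects is lost, because Section 17.2 rests that number on two previous studies with the same method.

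**Conclusion.** The point holds conditionally. As an ordinary product × time ANOVA, the planned test of product on plaque pH has the wrong error term, and its type I error could lie anywhere from about 0.5% to 51% over the assumed shares. The same mechanism applies to buffer capacity and saliva pH, with a different multiplier where there are fewer readings. As product × subject, or as a repeated-measures ANOVA, the test is close to nominal without a period effect. With an assumed trend of 0.25 SD per visit it is conservative (0.3% to 4.4%), with some loss of power. The sizes rest on the assumed variance shares, the assumed trend and, for power, a uniform 0.6 SD shift in one product. The degrees of freedom and the direction rule (7V against S) follow from the design alone.

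**What to change.** In Section 17.1 and in the synopsis, replace the two-way ANOVA for plaque pH, buffer capacity and saliva pH with a crossover mixed model: product, period, time and product × time as fixed effects, subject and subject-by-visit as random effects, sequence optional. If one summary per visit is analysed instead, use product + period + subject. Report product differences with 95% confidence intervals from that model. Settle this before any data are analysed.

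Naming a repeated-measures two-way ANOVA would be a smaller edit that restores the subject-level error term, but it would still leave period out. The cost is protocol wording and possibly software other than PRISM 8. No extra subjects, visits or measurements are needed.

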### 11.1 Recording of data

The PI will provide the Sponsor with all data produced during the study from the scheduled study assessments. The PI ensures the accuracy, completeness, legibility, and timeliness of the data reported to the Sponsor in the CRF and in all required reports.

The different study assessments will be collected in the following order:

1. Dental plaque acidogenicity
2. Salivary buffer capacity
3. Effects on oral mucosa
4. Subjectively perceived salivary stimulation
5. Collection of saliva

Subjects will be scheduled for three usage visits (Visits 2-4), with at least three days between each visit. For plaque acidogenicity, assessments will be performed before placement of the IP and at 2, 5, 10, 15, 20, 30, and 45 minutes afterwards. Allowed deviations for these time points are  $\pm 1$  minutes for the time points 0-15 minutes and  $\pm 2$  minutes for the time points 20-45 minutes. For assessments of salivary buffer capacity, effects on the oral mucosa, and subjectively perceived salivary stimulation, allowed deviations will be  $\pm 2$  minutes.

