## 11.4 Assessments related to secondary endpoints

### 11.4.1 *Buffer capacity*

The buffering capacity of saliva will be assessed at baseline (0 minutes), before use of the IP, and at 15, 30, and 45 minutes of usage. Unstimulated saliva, passively dropping saliva, will be collected at each time point. Then, 3 mL of 0.001 M HCl and 1 drop of octyl alcohol will be added to 1 mL of saliva. The sample will be aerated for 20 minutes, after which the final pH will be measured. The date and time of collection of each sample and the assessed pH levels will be recorded in the CRF.

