### 11.4.2 *Effects on oral mucosa*

The effects on the oral mucosa will be assessed before use of the IP and after 45 minutes of usage. The effects, in the form of redness and mechanical irritation, will visually be graded as: no effect, mild effect, and severe effect. Photos will be taken before and after usage of each IP to enable a more detailed comparison of the effects. The date and time of visual examination and assessed grading will be recorded in the CRF.

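### Ordinary Pearson correlation at p<0.05 is planned between variables that repeat within 12 subjects, and nothing prevents repeated readings from being pooled as independent pairs

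*Protocol*

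**What the plan says.** Section 17.1 of the protocol states that relationships between the collected variables "will be analyzed using Pearson correlation coefficient". The same section says that a p-value below 0.05 "is considered statistically significant", adds "No adjustment for multiple comparisons will be made", and assigns all analysis to PRISM 8. The synopsis repeats this. Neither place names the pairs of variables, the unit of analysis (reading, visit or subject) or a method for repeated measures.

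The data structure is set elsewhere in the protocol:

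- Section 8.1: "The study will include 12 randomized and fully evaluable subjects".
- Section 11.1: "Subjects will be scheduled for three usage visits (Visits 2-4), with at least three days between each visit".
- Section 11.3.1: plaque pH at four sites, at baseline and seven later times, at each usage visit.
- Section 11.4.1: buffer capacity at baseline and "at 15, 30, and 45 minutes of usage".
- Section 11.4.3: the salivary stimulation VAS once per usage visit, after 30 minutes.

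**The concern.** The usual test of a Pearson coefficient assumes that the pairs are independent. Here they are not, unless the data are first reduced to one pair per subject. No outcome variable has a natural single value per subject; even the VAS, the least repeated, gives three. An analyst who follows 17.1 must therefore either collapse the data by a rule that the protocol does not give, or pool the repeats.

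Pooling has two effects. It overstates the amount of information, so p-values are too small when both variables differ systematically between subjects. It also mixes association between subjects with association within a subject over visits and times, which makes the coefficient itself hard to interpret. At stake is that a relation between, say, plaque pH and a saliva measure is declared significant in the study report when it reflects only that the same 12 people were measured many times.

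**Working it through.** The plan gives no figure to reproduce. It has no power, target correlation or ICC for this analysis.

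**Inputs from the protocol.** 12 subjects; 3 usage visits; alpha 0.05 (taken as two-sided, since sidedness is not stated). Plaque pH and buffer capacity share the times 0, 15, 30 and 45 minutes. The VAS is taken once per visit.

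**Numbers of pairs if readings are pooled.**

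- One pair per visit (any pair with the VAS): 12 × 3 = 36, so m = 3 per subject.
- One pair per common time (plaque pH averaged over sites, against buffer capacity): 12 × 3 × 4 = 144, so m = 12 per subject.

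**Assumption.** The ICC of each variable is not in the documents. Values from 0.3 to 0.7 are used, with one unequal case.

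**Model.** Two truly unrelated variables, each with a subject effect: x = √ICCx·u + √(1−ICCx)·e, and y likewise with its own independent terms. Test: t = r·√((n−2)/(1−r²)) on n−2 degrees of freedom, with n = 12m. Each cell has 20,000 runs.

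| ICC of x, y | 36 pairs | 144 pairs | One mean per subject (n = 12) |
|---|---|---|---|
| 0, 0 | 5.0% | 5.0% | 5.1% |
| 0.3, 0.3 | 7.1% | 15.7% | 4.8% |
| 0.5, 0.5 | 10.7% | 30.9% | 5.2% |
| 0.7, 0.7 | 17.3% | 45.5% | 4.9% |
| 0.5, 0.2 | 7.2% | 16.2% | 5.0% |

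A separate simulation of 8,000 runs gave 7.2%, 11.1% and 17.8% for 36 pairs, and 16.0%, 30.3% and 44.5% for 144 pairs, at equal ICCs of 0.3, 0.5 and 0.7.

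**Check by formula.** Pooling inflates the null variance of r by about V = 1 + (m−1)·ICCx·ICCy, so the rejection rate is about 2Φ(−1.96/√V).

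- ICCs 0.5 and 0.5, m = 3: V = 1 + 2 × 0.25 = 1.5, about 11%.
- ICCs 0.5 and 0.5, m = 12: V = 1 + 11 × 0.25 = 3.75, about 31%.
- ICCs 0.5 and 0.2, m = 3: V = 1 + 2 × 0.10 = 1.2, about 7%.
- ICCs 0.5 and 0.2, m = 12: V = 1 + 11 × 0.10 = 2.1, about 18% (16% by simulation).

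V depends on the product of the two ICCs. If either is near zero, there is essentially no inflation.

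**Size of r that passes p<0.05.** |r| = 0.576 for n = 12, 0.329 for 36 pooled pairs and 0.164 for 144 pooled pairs.

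**The case against.** The strongest reply is that the protocol never says that readings will be pooled. Section 17.5.1 already averages plaque pH over the four sites, so some reduction is foreseen. With one value per subject, Pearson holds its level. Section 17 claims to give only principal features, and the unit of analysis for a supportive correlation can be set in a statistical analysis plan. No objective or endpoint, and no endpoint section in 17.5 to 17.7, names a correlation. Product comparisons rest on ANOVA with Tukey's test.

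Most of this stands, and it makes the point conditional and minor. It does not remove it. Averaging over sites leaves times and visits unreduced. The method and the threshold are fixed in the protocol itself, without a condition that would make them valid for repeated data.

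Three stronger readings are tempting and are not supported:

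- A reader might infer that the p-values are bound to be wrong. They are wrong only if repeats are pooled and both variables cluster by subject.
- A reader might infer that every collected variable will be correlated. The text refers to different collected variables and lists no pairs.
- A reader might infer that the mucosal grade, which "will visually be graded as: no effect, mild effect, and severe effect", is destined for Pearson and makes p-values too small. Section 17.6.2 plans grading, photographs and a descriptive text for it, with no correlation. In simulation, a three-level variable alone left the error rate at 5.2%, both with 12 values and with 36 independent points. The 9.2% seen with 36 points at ICC 0.5 comes from clustering.

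**Conclusion.** The concern holds in conditional form. Section 17.1 fixes a plain Pearson test at p<0.05 for a design in which every outcome variable repeats within 12 subjects, and nothing in the text rules out pooling. If readings are pooled, the type I error at nominal 5% is about 7% to 18% with 36 pairs and about 16% to 45% with 144 pairs, for assumed ICCs of 0.3 to 0.7 in both variables. At ICCs of 0.5 and 0.2 it is about 7% and 16%. One value per subject gives about 5%.

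The 144-pair figures apply only to variables measured at the four common times, such as plaque pH with buffer capacity. For any pair with the VAS, the 36-pair figures apply. The ICCs are assumptions, and the model ignores time trends within a visit and product effects. Severity is minor: a wrong p-value here would mislead in the report but would not change the primary or any secondary comparison. The documents do not say that correlations will be used as evidence for a product difference.

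**What to change.** In section 17.1 and the synopsis, replace the sentence on Pearson correlation by one that names the variable pairs and either correlates one predefined value per subject (n = 12) or uses a repeated-measures (within-subject) correlation. State that estimates will be reported with 95% confidence intervals as exploratory, without a claim of significance.

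The two options answer different questions: the first is about differences between subjects, the second about changes within a subject. The plan should say which is wanted.

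The cost is one sentence in each place. The n = 12 version needs no new software but is less precise. The within-subject version uses more of the data but may need software other than PRISM 8, in which case the statement that all analysis is done in that package must also change.
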